9.5.2 Method of Detecting AEs and SAEs

Care will be taken not to introduce bias when detecting AEs and/or SAEs. Open-ended and non-leading verbal questioning of the subject is the preferred method to inquire about AE occurrences.

9.5.3 Follow-up of AEs and SAEs

After the initial AE/SAE report, the Investigator or designee is required to proactively follow each subject at subsequent visits/contacts. All SAEs, will be followed until resolution, stabilization, the event is otherwise explained, or the subject is lost to follow-up (as defined in Section 7.3). Further information on follow-up procedures is given in [Appendix 3](#).

9.5.4 Regulatory Reporting Requirements for SAEs

- Prompt notification by the Investigator or designee to the Sponsor of an SAE is essential so that legal obligations and ethical responsibilities toward the safety of subjects and the safety of a study treatment under clinical investigation are met.
- The Sponsor has a legal responsibility to notify both the local regulatory authority and other regulatory agencies about the safety of a study treatment under clinical investigation. The Sponsor will comply with country-specific regulatory requirements relating to safety reporting to the regulatory authority, IRBs, and Investigators.

- Investigator safety reports must be prepared for suspected unexpected serious adverse reactions (SUSARs) according to local regulatory requirements and Sponsor policy and forwarded to Investigators as necessary.
- An Investigator who receives an Investigator safety report describing an SAE or other specific safety information (eg, summary or listing of SAEs) from the Sponsor will review and then file it along with the Investigator's Brochure and will notify the IRB, if appropriate according to local requirements.

9.5.5 Pregnancy

- Details of all pregnancies in female subjects will be collected after the start of study treatment and until 1 month after the last dose.
- If a pregnancy is reported, the Investigator should inform the Sponsor within 24 hours of learning of the pregnancy and should follow the procedures outlined in [Appendix 6](#).
- Abnormal pregnancy outcomes (eg, spontaneous abortion, fetal death, stillbirth, congenital anomalies, and ectopic pregnancy) are considered SAEs.

9.6 Treatment of Overdose

The Sponsor does not recommend specific treatment for an overdose. Washing with conventional cleanser and water will remove the product.

The subject, or the parent or guardian, should notify the Investigator of any overdose.

In the event of an overdose, the Investigator should:

1. Contact the Medical Monitor immediately.
2. Closely monitor the subject for any AE/SAE.
3. Document the quantity of the excess dose as well as the duration of the overdose in the CRF.

Decisions regarding dose interruptions will be made by the Investigator in consultation with the Medical Monitor based on the clinical evaluation of the subject.

9.7 Pharmacodynamics

Pharmacodynamics parameters are not evaluated in this study.

9.8 Genetics

Genetics are not evaluated in this study.

9.9 Biomarkers

Biomarkers are not evaluated in this study.

9.10 Health Economics/Medical Resource Utilization and Health Economics

Health Economics/Medical Resource Utilization and Health Economics parameters are not evaluated in this study.

10.0 STATISTICAL CONSIDERATIONS

10.1 Statistical Hypotheses

No formal statistical hypothesis testing is planned for this study. All analyses will be considered exploratory and descriptive.

10.2 Sample Size Determination

The study will enroll and dose 36 subjects, in 3 age cohorts of 12 subjects:

- Cohort 1: subjects aged 2 to 5 years old.
- Cohort 2: subjects aged 6 to 11 years old.
- Cohort 3: subjects aged 12 to 17 years old.

The sample size is not based on statistical considerations but is typical for studies of this nature, and is considered adequate to characterize the distribution of the planned endpoints. Any statistical testing will be considered exploratory and descriptive.

10.3 Populations for Analyses

For purposes of analysis, the analysis sets in [Table 10.1](#) are defined.

Table 10.1 Analysis Sets

Analysis Set	Description
Intent to Treat (ITT) population	All subjects who are enrolled and take at least 1 dose of study treatment. The ITT population will be the primary population for safety and efficacy assessments.
Per Protocol (PP) population	All subjects in the ITT population without any protocol deviations that may have an impact on the efficacy assessments. The PP population will be the supportive population for efficacy assessments.

10.4 Statistical Analyses

The Statistical Analysis Plan will be developed and finalized before database lock and will describe the subject analysis sets to be included in the analyses, and procedures for accounting for missing, unused, and spurious data. This section is a summary of the planned statistical analyses of the primary and secondary endpoints.

All analyses, summaries, and listings will be performed using SAS® software (version 9.3 or higher).

The following descriptive statistics will be used as applicable to summarize the study data unless otherwise specified:

- Continuous variables: sample size (n), mean, standard deviation, median, minimum (min), and maximum (max).
- Categorical variables: frequencies and percentages.

Individual subject data will be presented in listings.

10.4.1 Efficacy Analyses

All efficacy analyses will be performed on the ITT and PP populations, for overall and by age cohorts (2 to 5 years, 6 to 11 years, and 12 to 17 years).

Summary statistics will be provided for the vIGA-AD scale, EASI score (total and by component), POEM score (total and by component) and the ItchMan scale, and changes from baseline at each visit. The frequency and percentage of subjects who have achieved clear (0) or almost clear (1) on the vIGA-AD scale will also be provided at each visit.

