4.6 Study Stopping Criteria

Dosing for any individual subject will be stopped if:

- The subject experiences a possibly drug-related SAE.
- The subject experiences a possibly drug-related significant non-serious adverse event (AE), which in the opinion of the Principal Investigator, Chief Investigator, Medical Monitor, or

Sponsor's medical representative, warrants discontinuation from the study for that subject's wellbeing. The occurrence of significant non-serious AEs as described above will require that further dosing of other subjects be evaluated by the Chief Investigator, the Medical Monitor and the Sponsor's Medical Advisor to determine study discontinuation.

- The subject's atopic dermatitis worsens and requires alternative or supplemental medication during the study (see [Section 6.8](#) for allowed treatments).
- The subject or his/her parent or guardian choose to discontinue for any reason.

Dosing for a cohort will be stopped if:

- A subject experiences a possibly drug-related SAE.
- More than 2 subjects experiences a possibly drug-related significant non-serious AE, which in the opinion of the Principal Investigator, Chief Investigator, Medical Monitor, or Sponsor's medical representative, warrants discontinuation from the study for that subject's wellbeing. The occurrence of significant non-serious AEs as described above will require that further dosing of other subjects be evaluated by the Chief Investigator, the Medical Monitor and the Sponsor's Medical Advisor to determine study discontinuation.

The study will be stopped if:

- More than 1 subject experiences a drug-related SAE.

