5.1 Inclusion Criteria

Subjects are eligible to be included in the study only if all of the following criteria apply:

1. Male and female subjects 2 to 17 years of age, inclusive.
2. Confirmed diagnosis of atopic dermatitis according to the Hanifin and Rajka criteria.
3. A minimum of 10% but no more than 60% of the subjects' body surface area (see [Appendix 6](#) for guidance) is affected by atopic dermatitis (affected is defined by physical examination findings: erythema, edema, scaling, lichenification, and excoriation; with the excoriation serving as the physical examination correlate of pruritus).
4. A vIGA-AD scale of 2 or 3 at Screening and Baseline.
5. Subject, or the parent or guardian, to provide written informed consent and authorization for protected health information disclosure.
6. Subjects must be generally in good health based on Investigator's assessment (other than atopic dermatitis).
7. Normal vital signs, or with no clinically significant vital signs that in the opinion of the Investigator, would place the subject at increased risk or would confound the objectives of the study.
8. Females must not be pregnant, as confirmed by negative urine pregnancy testing. Female subjects aged ≥ 11 years old, or female patients < 11 years old who have started menstruating, will have urinary pregnancy test performed at Screening and prior to the first dose with negative results in order to participate in the study. Females must either practice abstinence from heterosexual contact or use one of the highly effective contraceptive options described in the [Appendix 5](#).
9. Male subjects of reproductive potential, must be willing to practice effective contraception during the study while receiving study treatment from Day 1 and for 7 days after the last study visit (Day 28).
10. Ability to comprehend and comply with study procedures.
11. Agree to commit to participate in the current protocol.
12. Provide written informed consent prior to any study procedure being performed.

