6.8 Rescue Medication Permitted During the Study

Over the course of the study, the Investigator will monitor and evaluate subject's condition and determine whether rescue therapy may be necessary. The use of medications to treat a subject's atopic dermatitis during the study will be permitted if the parent, guardian or medical professional determines that it becomes medically necessary. Such rescue treatment should not exceed 7 days. If a subject requires treatment for more than 7 days or requires systemic therapy, they should be discontinued from the study. Medications permitted are listed in Table 6.3.

Study staff must be notified of the use of any medication as soon as feasible. The details of the medication should be recorded in the study diary and transferred to the CRF. Details recorded should include medication name, date of administration, dosage, and number of applications.

Table 6.3 Permitted Rescue Medication

Class 4 – Mid-strength	
Clocortolone pivalate (0.1%)	Cloderm® Cream
Mometasone furoate (0.1%)	Elocon® Cream
Triamcinolone acetonide (0.1%)	Aristocort® A Cream, Kenalog® Ointment
Betamethasone valerate (0.1%)	Valisone Ointment
Fluocinolone acetonide (0.025%)	Synalar® Ointment
Class 5 – Lower Mid-strength	
Fluticasone propionate (0.05%)	Cutivate® Cream/Cutivate Lotion
Prednicarbate (0.1%)	Dermatop® Cream
Hydrocortisone probutate (0.1%)	Pandel® Cream
Triamcinolone acetonide (0.1%)	Aristocort A Cream, Kenalog Lotion
Fluocinolone acetonide (0.025%)	Synalar Cream
Class 6 – Mild	
Alclometasone dipropionate (0.05%)	Aclovate® Cream/Ointment
Desonide (0.05%)	Verdeso™ Foam, Desonate Gel™
Triamcinolone acetonide (0.025%)	Aristocort A Cream, Kenalog Lotion
Hydrocortisone butyrate (0.1%)	Locoid Cream/Ointment
Fluocinolone acetonide (0.01%)	Derma-Smoothe/FS® Scalp Oil, Synalar Topical Solution
Class 7 – Least potent	
Hydrocortisone (2%/2.5%)	Nutracort® Lotion, Synacort Cream
Hydrocortisone (0.5 to 0.1%)	Cortaid® Cream/Spray/Ointment and many other over-the-counter products

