10.4.3 Missing Data

Data from subjects who withdraw from the study, including AEs and any follow-up, will be included in the analyses of all outcomes.

Missing data will not be imputed.

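### Sections 4.6 and 6.8 leave unclear whether a child on permitted steroid rescue is still on B244, and the vIGA-AD 0/1 summary counts scores after rescue as response

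*Protocol*

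**What the plan says.** **Rescue.** Protocol section 6.8 says that medication for atopic dermatitis "during the study will be permitted if the parent, guardian or medical professional determines that it becomes medically necessary". Table 6.3 lists the permitted products, all class 4 to 7 topical corticosteroids. On duration: "Such rescue treatment should not exceed 7 days". On leaving the study: "If a subject requires treatment for more than 7 days or requires systemic therapy, they should be discontinued from the study". Drug, date, dosage and number of applications go into the diary and from there to the CRF.

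**Stopping.** Section 4.6 stops dosing for an individual child whose atopic dermatitis "worsens and requires alternative or supplemental medication during the study (see [Section 6.8](#) for allowed treatments"). It gives no minimum duration. Section 7.1 simply refers back to 4.6.

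**Analysis.** Entry requires "A vIGA-AD scale of 2 or 3 at Screening and Baseline". Section 10.4.1 summarises vIGA-AD, EASI, POEM and ItchMan at each visit, in ITT and PP, overall and by age cohort, and adds that the "percentage of subjects who have achieved clear (0) or almost clear (1) on the vIGA-AD scale will also be provided at each visit". Rescue is not mentioned. In section 10.3, ITT is the primary population and PP is defined as "All subjects in the ITT population without any protocol deviations that may have an impact on the efficacy assessments". Section 10.4.3 adds: "Data from subjects who withdraw from the study, including AEs and any follow-up, will be included in the analyses of all outcomes". Missing values are not imputed. Section 10.1 plans no formal test.

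**The concern.** There are two linked problems.

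The first concerns conduct. For a child given a short permitted steroid course, 4.6 can be taken to end B244, while 6.8 implies that the child carries on. With about 6 centres planned, sites could act differently. The reading determines the child's B244 exposure after rescue and who counts as having discontinued treatment. That touches the primary safety description as well as efficacy.

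The second concerns reading the efficacy tables. There is no control arm. A vIGA-AD score of 0 or 1 during or after a steroid course enters the responder percentage in the same way as one reached on B244 alone. A child who enters at grade 2 needs to fall by only one grade. If PP, the supportive analysis, keeps the same score, comparing ITT with PP does not reveal the problem.

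**Working it through.** **Step 1. Sections 4.6 and 6.8 side by side, for permitted rescue of 7 days or less.**

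| | Trigger | Consequence |
|---|---|---|
| 4.6 | Worsening that needs other or added medication, any duration | Dosing stopped; refers to 6.8 |
| 6.8 | More than 7 days of treatment, or systemic therapy | Discontinued from the study |

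The cross-reference in 4.6 has two readings. (a) Treatments allowed by 6.8 are exempt, so B244 continues. (b) Treatments allowed by 6.8 are the ones that may be given once dosing stops, so B244 ends while the child remains under follow-up. Neither 6.8 nor 7.1 chooses between them.

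**Step 2. Does PP remove the rescued child?** PP removes subjects for protocol deviations that may affect efficacy. Rescue within 6.8 is expressly permitted. Appendix 4 calls use of an excluded medication a violation, but lists topical corticosteroids only for the 2 weeks before Baseline. Permitted rescue is therefore not plainly a deviation, and PP may keep the child.

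**Step 3. Would visits fall inside a rescue course?** Take nominal visits on Days 7, 14, 21 and 28 and possible rescue start days 2 to 28, which gives 27 start days. A course of L days starting on day s covers a visit v if s ≤ v ≤ s + L − 1.

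- L = 7: at least one visit falls inside the course for 27 of 27 start days.
- L = 5: 20 of 27.
- L = 3: 12 of 27.

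The ±2-day visit window is ignored here. A full permitted course will therefore normally overlap a scored visit.

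**Step 4. Size per child.** The protocol has 3 cohorts of 12, and 3 × 12 = 36, which agrees with its stated total. It gives no other figure to reproduce on this point. One child scored 0/1 after rescue contributes:

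- 1/12 = 8.3 percentage points in a cohort;
- 1/36 = 2.8 percentage points overall.

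**Step 5. Illustration with assumed counts.** The protocol gives neither a rescue rate nor a response rate. Suppose one third are scored 0/1 at a visit, and k of those scores follow the start of rescue. With those visits counted as non-response, the rate is (responders − k)/n:

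| k | Cohort, 4/12 = 33.3% as written | Overall, 12/36 = 33.3% as written |
|---|---|---|
| 0 | 4/12 = 33.3% | 12/36 = 33.3% |
| 1 | 3/12 = 25.0% | 11/36 = 30.6% |
| 2 | 2/12 = 16.7% | 10/36 = 27.8% |
| 3 | 1/12 = 8.3% | 9/36 = 25.0% |

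For k from 0 to 3 the difference is 0 to 25.0 points in a cohort and 0 to 8.3 points overall.

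**The case against.** **Much of this belongs in the SAP.** Section 10.4 describes itself as a summary and leaves the analysis sets to the SAP. Handling of scores after rescue, and the deviations that remove a subject from PP, are normal SAP content. This largely stands: the lack of a rescue rule in the protocol would be a weak point by itself. It does not reach the 4.6/6.8 question, which concerns what sites do with the child.

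**Section 10.4.1 is not wrong.** An observed-value summary on ITT is a coherent descriptive choice, and counting visits after rescue as non-response is one strategy among several. This stands too, which is why the observed summaries should stay and only one should be added.

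**Sections 4.6 and 6.8 can be read consistently.** If the cross-reference is an exemption, the two sections agree. A reader might infer an outright contradiction. The text does not support that; it shows an ambiguity. But the opposite reading is equally open to a site.

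**Rescued children can be found anyway.** Individual data are listed, concomitant medication is listed, and cohorts have only 12 children. That limits the harm but does not change the tabulated percentages.

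**Stronger inferences to avoid.** A reader might take section 10.4.3 to mean that Early Termination scores of a child discontinued for prolonged or systemic treatment enter the by-visit response rates. That section does not mention rescue, and the protocol does not assign an Early Termination assessment to a visit. A reader might also try to state a shift in mean vIGA-AD change. That would assume the child would otherwise have stayed at the entry grade, which is not justified when rescue follows worsening.

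**Conclusion.** The point holds in a limited form. The firmer part is that 4.6 and 6.8 do not say clearly whether a child on permitted rescue is on or off B244, and only the protocol can settle this. No view is taken here on which rule is right.

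The lesser part is that 10.4.1, followed as written, counts a 0/1 score after permitted steroid as response, and PP may not remove it. The size is 8.3 points per child in a cohort or 2.8 points overall. It rests on assumed counts and is zero if no rescued child is scored 0/1.

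Weight is low. Efficacy is exploratory, no test is planned, and no error rate or power is affected. It would go too far to infer that the response rates will be materially inflated, since the protocol gives no rescue rate. Setting rescue apart would not isolate a B244 effect either: it removes one known source of distortion from an uncontrolled comparison with Baseline.

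**What to change.** 1. Reconcile sections 4.6 and 6.8 so that together they give one answer on whether a child receiving rescue permitted by 6.8 is on or off B244. The choice is the sponsor's.
2. In section 10.4.1, keep the observed-data summaries and add one vIGA-AD 0/1 summary in which visits after the start of rescue count as non-response. Applied to visits with an observed score, this reclassifies data and does not conflict with the no-imputation rule in 10.4.3.

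The list of deviations that remove a subject from PP can stay with the SAP.

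The cost is a wording change and one derived flag, built from rescue dates that section 6.8 already sends to the CRF. No new data are collected. The downside is that the added response rate may be lower than the observed one.

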10.4.2 Safety Analyses

All safety analyses will be performed on the ITT population.

All safety assessments, including TEAEs, vital signs and weight, physical examinations, medical examination pregnancy test results and concomitant medication will be listed and as appropriate summarized with descriptive statistics.

Treatment-emergent adverse events are defined as AEs that first occurred or worsened in severity after the first administration of study treatment.

Adverse events will be coded using the Medical Dictionary for Regulatory Activities (MedDRA). The numbers of TEAEs and incidence rates will be tabulated by preferred term and system organ class, for overall and by cohort.

Treatment-emergent AEs by maximum severity, TEAEs by relationship to study treatment, SAEs, TEAEs leading to death, and TEAEs leading to discontinuation of study treatment will be tabulated for overall and by age cohort.

All vital signs measurements, weight, and body mass index will be summarized for overall and by age cohort, using descriptive statistics at each visit for raw numbers and change from Baseline. The incidence of abnormal physical examination results will also be summarized using descriptive statistics.

10.4.3 Missing Data

Data from subjects who withdraw from the study, including AEs and any follow-up, will be included in the analyses of all outcomes.

Missing data will not be imputed.

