7.0 DISCONTINUATION OF STUDY TREATMENT AND SUBJECT DISCONTINUATION/WITHDRAWAL

7.1 Discontinuation of Study Treatment

The stopping criteria for the study are described in Section [4.6](#).

If a subject who does not meet enrollment criteria is inadvertently enrolled, that subject must be discontinued from study treatment and the Sponsor or Sponsor designee must be contacted. An exception may be granted in rare circumstances for which there is a compelling safety reason to allow the subject to continue. In these rare cases, the Investigator must obtain documented approval from the Sponsor or Sponsor designee to allow the subject to continue in the study.

Subjects who discontinue study treatment will not be replaced.

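### With no imputation and no stated rule for early leavers, Day 28 efficacy summaries can look better than they would over all treated children

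*Protocol*

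**What the plan says.** **Who leaves or stops.** Protocol section 4.6 stops an individual child's dosing if the child's "atopic dermatitis worsens and requires alternative or supplemental medication during the study", and refers to section 6.8. Section 6.8 allows listed topical rescue on study: "Such rescue treatment should not exceed 7 days". It then adds: "If a subject requires treatment for more than 7 days or requires systemic therapy, they should be discontinued from the study". Section 7.1 states "Subjects who discontinue study treatment will not be replaced".

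**What is recorded.** A child who withdraws before Day 28 is asked to attend an Early Termination visit (8.2.7). vIGA-AD, EASI, POEM and ItchMan are all recorded there. In Table 1.1 that visit has its own column, without a visit number or a window.

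**How it is analysed.** Section 10.4.1 summarises scores and changes from baseline by visit in the ITT and PP sets, and the "percentage of subjects who have achieved clear (0) or almost clear (1) on the vIGA-AD scale will also be provided at each visit". Section 10.4.3 makes two statements in sequence: "Data from subjects who withdraw from the study, including AEs and any follow-up, will be included in the analyses of all outcomes", and then "Missing data will not be imputed".

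**The concern.** Leaving the study is partly driven by the outcome being summarised. A child whose dermatitis worsens enough to need prolonged or systemic treatment is discontinued under 6.8, so the later scheduled visits have no value for that child. With no imputation, a Day 28 mean is taken over the children still attending, who have been selected for not doing badly. The same applies to the 0/1 percentage if its denominator is the children observed.

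The study has no control arm, so nothing in the data would reveal this tilt. The PP set is a subset of ITT and cannot bring the missing children back. At stake is how the exploratory efficacy results read, above all at Day 28 and within cohorts of 12, where one or two children move a percentage visibly.

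**Working it through.** **Reproducing the plan's figure.** The only figure that can be checked is the size: 3 cohorts × 12 = 36, which agrees with section 10.2. The protocol gives no dropout rate, response rate, effect size or standard deviation. The stop rates, responder counts and changes below are therefore assumptions.

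**Response rate.** Let n be the children dosed, k the leavers with no Day 28 value, and r the responders (vIGA-AD 0 or 1) at Day 28. Assume that no leaver would have been a responder.

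- Over all dosed: r / n
- Over observed: r / (n − k)

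Overall, n = 36 and r = 12, so the all-dosed rate is 12/36 = 33.3%. Assumed stop rates of 5%, 10%, 20% and 30% round to k = 2, 4, 7 and 11:

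- k = 2: 12/34 = 35.3%
- k = 4: 12/32 = 37.5%
- k = 7: 12/29 = 41.4%
- k = 11: 12/25 = 48.0%

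One cohort, n = 12 and r = 4, so the all-dosed rate is 4/12 = 33.3%:

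- k = 1: 4/11 = 36.4%
- k = 2: 4/10 = 40.0%
- k = 4: 4/8 = 50.0%

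**Mean change.** Let d be the proportion who leave. Assume that children who stay improve by 30% and leavers had worsened by 25% when last seen. The observed-case mean is −30% whatever d is. Over all dosed it is (1 − d)(−30) + d(+25):

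- d = 0.05: −28.5 + 1.25 = −27.25%
- d = 0.10: −27 + 2.5 = −24.5%
- d = 0.20: −24 + 5 = −19.0%
- d = 0.30: −21 + 7.5 = −13.5%

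**Chance that a cohort is affected.** At an assumed 10% stop rate, the chance of at least one such leaver among 12 is 1 − 0.9^12 = 0.718, about 72%.

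**Reading the sections together.** Section 4.6 stops dosing for worsening that needs other medication, while 6.8 keeps a child on short topical rescue in the study. The two do not agree on what happens to a child who needs short rescue. Section 7 treats stopping treatment (7.1) separately from leaving the study (7.2), but nothing says whether a child off treatment keeps attending visits. Section 10.4.3 promises to include withdrawn subjects' data in every outcome analysis, and 10.4.1 does not say how that is met in a Day 28 row. Section 10.4 lists n among the summaries for continuous variables, but only frequencies and percentages for categorical ones, so the 0/1 denominator remains open.

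**The case against.** A reader might infer three stronger things, none of which the protocol supports.

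- **That 4.6 takes worsening children out of the study.** Its list concerns dosing, and 6.8 keeps children on short topical rescue in the study. Some worsened children will therefore appear in later visits, with scores that also reflect the rescue treatment.
- **That ET values reach no summary.** ET is a named post-baseline visit with all four scales. Section 10.4.1 does not exclude it, and 10.4.3 says withdrawn subjects' data are included. What can be said is that ET values are assigned to no scheduled visit. Even if ET has its own row, the Day 28 row still lacks those children.
- **That later visits describe mainly children who did not worsen.** That depends on a stop rate the protocol does not give.

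The denominator objection also has force. Efficacy is analysed on ITT, which is all dosed children, so 12/36 fits the text as well as 12/25 does. The inflated rate arises only under the observed-case reading.

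The strongest general objection is that ET mapping and denominators are ordinary SAP content, that 10.4 defers missing-data procedures to the SAP, and that observed-case reporting is defensible in a descriptive study of 36 children. Most of this stands. It does not dispose of the point, because the protocol itself fixes the no-imputation rule. An SAP that counted leavers as non-responders, or used an ET value at end of treatment, could be read as departing from it.

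The proposed additions have limits too. Counting leavers as not achieving 0/1 understates response if some left while improving, and a Day 28-or-ET row mixes different treatment durations. Both should therefore stand beside the observed-case tables and not replace them.

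**Conclusion.** The concern holds in a limited form. Exit from the study is linked to worsening, leavers are not replaced, and imputation is ruled out. Day 28 means, and the 0/1 rate if taken over observed children, can therefore look better than they would over all treated children. The direction is clear for children who leave because they worsened. It need not apply to those who leave for other reasons.

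The size cannot be derived from the protocol. On the assumed range of 2 to 11 leavers of 36, with none a responder, 33% reads as 35% to 48%. If few children leave, the effect is small. Efficacy is exploratory and descriptive, every post-baseline visit is reported, and the primary objective is safety. This is a worthwhile and cheap improvement, and no primary conclusion depends on it.

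**What to change.** In sections 10.4.1 and 10.4.3, keep the observed-case visit tables, show n for every scale at every visit, and add:

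1. The vIGA-AD 0/1 percentage at each visit over all ITT subjects. Subjects with no value at that visit because they left the study count as not achieving 0/1; children still attending keep their observed score.
2. One end-of-treatment row for vIGA-AD, EASI, POEM and ItchMan, using the Day 28 value or, for those who left early, the ET value. Label it supportive.

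Reword 10.4.3 so that the no-imputation rule does not forbid these two summaries.

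Separately, the sponsor must reconcile 4.6 with 6.8 on what happens to a child who needs short rescue, and should state whether children off treatment keep attending visits. Which rule applies is the sponsor's clinical decision.

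The cost of the analysis change is a few sentences, one extra percentage per visit and one extra row per scale, all from data already collected. The downside is a somewhat less favourable response rate.
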